5.1. Analysis Specifications

5.1.1. Level of Significance

All statistical procedures to test superiority hypotheses will be performed at a 2-sided significance level of 0.05 and 1-sided at a significance level of 0.025 for non-inferiority. This study is designed to maintain an overall Type I error of 0.05 or less for the primary analysis and major secondary analyses. Nominal p-values will be reported for other secondary analyses.

5.1.1.1. Multiplicity Adjustment for Testing Procedures

The primary endpoint in this study is the proportion of subjects who achieve a PASI 90 response at Week 48. The primary analyses will be evaluated by a non-inferiority test with a non-inferiority margin of 10% followed by a superiority test between the guselkumab 100 mg treatment group and the secukinumab 300 mg group.

In addition, there are 6 major secondary endpoints in this study to be compared between the guselkumab 100 mg group and the secukinumab 300 mg group:

- The non-inferiority test comparing guselkumab with secukinumab for the proportion of subjects achieving a PASI 75 response at both Week 12 and Week 48 will be performed. If non-inferiority is established, the superiority test on this endpoint will be performed.
- The non-inferiority test comparing guselkumab with secukinumab for the proportion of subjects achieving a PASI 90 response at Week 12 will be performed.
- The non-inferiority test comparing guselkumab with secukinumab for the proportion of subjects achieving a PASI 75 response at Week 12 will be performed.
- The non-inferiority test comparing guselkumab with secukinumab for the proportion of subjects achieving a PASI 100 response at Week 48 will be performed. If non-inferiority is established, the superiority test on this endpoint will be performed.
- The non-inferiority test comparing guselkumab with secukinumab for the proportion of subjects achieving an IGA score of cleared (0) at Week 48 will be performed. If non-inferiority is established, the superiority test on this endpoint will be performed.
- The non-inferiority test comparing guselkumab with secukinumab for the proportion of subjects achieving an IGA score of cleared (0) or minimal (1) at Week 48 will be performed. If non-inferiority is established, the superiority test on this endpoint will be performed.

In order to control the overall Type 1 error rate, the primary analysis and major secondary analyses will be tested in a fixed sequence as ordered above. That is, the first major secondary analysis will be performed only if the primary endpoint is positive for both non-inferiority and superiority, and each subsequent analysis will be performed only if the preceding analysis in the sequence is positive.

5.1.2. Definition of the Efficacy Endpoints and Calculation of the Efficacy Instruments

5.1.2.1. Investigator's Global Assessment

The Investigator's Global Assessment (IGA) documents the investigator's assessment of the subject's psoriasis at a given time point. Overall lesions are graded for induration, erythema, and scaling. The patient's psoriasis is assessed as cleared (0), minimal (1), mild (2), moderate (3), or severe (4).

Efficacy endpoints related to the IGA score are defined below:

IGA cleared responder

Subjects who achieve an IGA score of cleared (0) will be considered IGA cleared responders.

IGA cleared or minimal responder

Subjects who achieve an IGA score of cleared (0) or minimal (1) will be considered IGA cleared or minimal responders.

IGA mild or better responder

Subjects who achieve an IGA score of cleared (0), minimal (1), or mild (2) will be considered IGA mild or better responders.

5.1.2.2. Psoriasis Area and Severity Index

The PASI is a system used for assessing and grading the severity of psoriatic lesions and their response to therapy. In the PASI system, the body is divided into 4 regions: the head, trunk, upper extremities, and lower extremities. Each of these areas is assessed separately for the percentage of the area involved, which translates to a numeric score that ranges from 0 (indicates no involvement) to 6 (90%-100% involvement), and for erythema, induration, and scaling, which are each rated on a scale of 0 to 4. The PASI produces a numeric score that can range from 0 (no psoriasis) to 72. A higher score indicates more severe disease.

Efficacy endpoints related to the PASI score are defined below:

PASI 50 Responder

Subjects with $\geq 50\%$ improvement in PASI from baseline will be considered PASI 50 responders.

PASI 75 Responder

Subjects with $\geq 75\%$ improvement in PASI from baseline will be considered PASI 75 responders.

PASI 90 Responder

Subjects with $\geq 90\%$ improvement in PASI from baseline will be considered PASI 90 responders.

PASI 100 Responder

Subjects with 100% improvement in PASI from baseline (ie, a PASI score of 0) will be considered PASI 100 responders.

5.1.3. Data Handling Rules

The following treatment failure rules and data handling rules will be applied to the PASI and IGA related efficacy analyses in this study.

5.1.3.1. Treatment Failure Criteria

Subjects who discontinue study agent due to lack of efficacy, an adverse event (AE) of worsening of psoriasis, or who started a protocol-prohibited medication/therapy during the study that could affect their psoriasis are considered as treatment failures.

The protocol-prohibited medications/therapies include:

Topical Therapies:

- Any topical therapies used for psoriasis (with the exception of topical moisturizers and shampoos containing tar or salicylic acid only)

Phototherapy or Systemic Therapies:

- Any systemic corticosteroid used for psoriatic arthritis or psoriasis with the exception of intra-articular corticosteroids.
- Any other anti-psoriatic systemic therapy or biologic therapy.
- Phototherapy of UVB or PUVA.
- Any other phototherapy for psoriasis.

5.1.3.2. Treatment Failure Rules

A subject who meets one or more of the treatment failure criteria specified in Section 5.1.3.1 will be considered a treatment failure from that point onward. The baseline values will be used for all directly measured endpoints regardless of the actual measurements. Zero will be assigned to improvement and percent improvement, and non-responder status will be assigned to binary response variables.

Treatment failure is assumed to have occurred at the earlier of the following dates:

- Date of discontinuation (DC) of study treatment due to lack of efficacy or an AE of worsening of psoriasis or
- Date of initiation of a protocol-prohibited medication/therapy during the study that could improve psoriasis

5.1.3.3. Missing Data Imputation

After the treatment failure rules are applied, the remaining missing data will be handled as follows for all of the efficacy analyses including the analyses at key visits (eg, Week 12 and Week 48) and over time:

- Non-responder imputation will be applied for binary endpoints.
- No imputation will be performed for continuous endpoints and the values will remain as missing.

5.2. Primary Efficacy Endpoint(s)**5.2.1. Definition**

The primary endpoint in this study is the proportion of subjects who achieve a PASI 90 response at Week 48. Refer to Section 5.1.2.2 for the definition of a PASI 90 responder.

5.2.2. Estimand

Population: subjects with moderate-to-severe plaque psoriasis who are randomized and treated with guselkumab 100 mg or secukinumab 300 mg.

Endpoint: the proportion of subjects who achieve a PASI 90 response at Week 48

Measure of Intervention: the effect of the initially randomized treatment regardless of what treatments are actually received. Non-responder status will be assigned if treatment failure criteria are met or data are missing.

5.2.3. Analysis Methods

The primary endpoint will be compared between the guselkumab 100 mg group and the secukinumab 300 mg group. In the primary efficacy analysis, data from all randomized will be analyzed according to their assigned treatment group (ie, full analysis set). The number and proportion of subjects who achieve a PASI 90 response at Week 48 will be summarized for each treatment group respectively.

To address the primary efficacy objective, the proportion of subjects achieving a PASI 90 response at Week 48 will be evaluated with a non-inferiority test followed by a superiority test. The following stepwise comparisons will be made to compare the efficacy of guselkumab to that of secukinumab at Week 48:

- a. First a non-inferiority test with a non-inferiority margin of 10% will be conducted. A non-inferiority margin of 10% was chosen based on a minimal clinically meaningful difference. This margin was also used as the non-inferiority margin for the ustekinumab psoriasis study C0743T12 and the guselkumab psoriasis CNTO1959PSO3001 and CNTO1959PSO3002 studies. In addition, in studies with biologic agents, placebo response rates for PASI 90 are consistently low (eg, <5% Cosentyx[®] SmPC, <5% STELARA SmPC, <5% guselkumab). Further, there is no placebo data at Week 48 for any clinical study of biologics. Therefore, the preservation of benefit for the Week 48 endpoints is based on the historic response rates of the active comparator, ie, secukinumab. Based on the 2 placebo-controlled Phase 3 secukinumab studies (FIXTURE and ERASURE), a PASI 90 response was estimated to occur in 64.6% (95% confidence interval [CI]: 60.7%, 68.6%) of subjects receiving secukinumab 300 mg at Week 48, whereby a 10% non-inferiority margin would preserve at least 80% of the secukinumab benefit.

To claim the non-inferiority of guselkumab to secukinumab, a 1-sided ($\alpha=0.025$) Z-test with Mantel-Haenszel (MH) weights adjusting for investigator site² will be used. That is, the lower bound of the 2-sided 95% confidence interval (CI) of $P1 - P2$ must be $\geq -10\%$, where $P1$ and $P2$ are the proportions of subjects achieving a PASI 90 response at Week 48 in the guselkumab 100 mg and the secukinumab 300 mg groups, respectively. The 2-sided 95% CI on the difference between guselkumab 100 mg and the secukinumab 300 mg groups will be calculated adjusting for investigator site after pooling using Mantel-Haenszel weights.² If non-inferiority is not established, no further test will be conducted and Step b will be skipped.

- b. If non-inferiority is established in Step a, the superiority test of guselkumab to secukinumab using the CMH chi-square test stratified by investigator site after pooling will be performed at a significance level of 0.05. The proportion difference between guselkumab 100 mg and the secukinumab 300 mg groups and its 2-sided 95% CI will be provided based on normal approximation with Mantel-Haenszel weights adjusting for investigator site.

If both the non-inferiority test and the superiority test are positive, the major secondary hypotheses comparing the guselkumab group and the secukinumab group will be tested sequentially. Otherwise, all remaining p-values will be considered nominal.

5.2.4. Data Handling

Subjects who meet treatment failure criteria specified in Section 5.1.3.1 prior to Week 48 will be considered PASI 90 nonresponders at Week 48. In addition, subjects with a missing PASI score at Week 48 or who do not return for evaluation at Week 48 will be considered PASI 90 nonresponders at Week 48.

5.2.5. Sensitivity Analysis

To assess the robustness of the primary endpoint analysis results, the following three sensitivity analyses will be conducted.

Sensitivity Analysis 1

For subjects who have a missing PASI score at Week 48, the score will not be imputed. That is, the analysis will be performed using observed data, after applying treatment failure rules (as defined in Section 5.1.3.2).

Sensitivity Analysis 2

The second sensitivity analysis will be performed by using multiple imputations (MI), after applying treatment failure rules (as defined in Section 5.1.3.2). The intermittent missing PASI scores which include PASI scores at Week 0, Week 4 through Week 48 will be imputed using the Markov Chain Monte Carlo (MCMC) algorithm with 200 imputed data sets and seed = 123 to make the missing data pattern monotone. The PASI 90 responses will then be derived based on the imputed score at or before Week 48. The remaining missing data for the PASI 90 response will be imputed with monotone logistic regression with treatment group, baseline PASI, investigator site and PASI 90 response status starting from Week 4 in the model with one imputed dataset and seed = 789 to fill in the remaining missing items in each of the 200 copies of datasets. If the model fails to converge, investigator site will not be included as an explanatory variable. The proportion difference of PASI 90 response at Week 48 adjusted for investigator site (pooling) using Mantel-Haenszel weight between the guselkumab 100 mg and the secukinumab 300 mg groups and its 95% CI combining multiple datasets will also be provided. In addition, the superiority test of guselkumab to secukinumab combining all the multiple imputation datasets using the CMH chi-square test stratified by investigator site will be performed at a significance level of 0.05.

Sensitivity Analysis 3

A generalized linear model with logit link for binary repeated measurement data will also be performed as a sensitivity analysis to compare the proportion of subjects responding to treatments at Week 48, after applying treatment failure rules (as defined in Section 5.1.3.2). The model will include baseline PASI score, treatment group, investigator site, visit starting from Week 4, the interaction of treatment group and visit, and the interaction of baseline PASI score

and visit as explanatory variables. If the model fails to converge, investigator site will not be included as an explanatory variable. The derived odds ratio on PASI 90 at Week 48 and its 95% CI will be provided. In addition, the proportion difference of PASI 90 response at Week 48 between the guselkumab 100 mg and the secukinumab 300 mg groups and its 95% CI will also be provided. For subjects who do not return for evaluation at any visit, the missing PASI score will not be imputed.

5.2.6. Subgroup Analysis

For each of the subgroups defined in Section 2.5, the proportion of subjects achieving a PASI 90 response at Week 48 by treatment group will be summarized, respectively. Under the assumption of normal distributions, the 95% confidence interval without adjusting for investigator site of the difference between the guselkumab 100 mg and the secukinumab 300 mg groups for the primary endpoint will also be provided. In addition, the proportion of PASI 90 responders at Week 48 by investigator site will be summarized.

5.2.7. Per Protocol Analyses

The primary analysis will also be performed on the per protocol analysis set defined in Section 2.4.1.2.

5.3. Major Secondary Endpoints

The analyses for the major secondary endpoints will be performed in the order listed in Section 5.1.1.1.

The sections below outline the analysis methods and the data imputation rules for the major secondary analyses to be performed.

5.3.1. Definition

There are 6 major secondary endpoints in this study to be compared between the guselkumab 100 mg group and the secukinumab 300 mg group:

- A PASI 75 response at both Week 12 and Week 48.
- A PASI 90 response at Week 12.
- A PASI 75 response at Week 12.
- A PASI 100 response at Week 48.
- An IGA score of cleared (0) at Week 48.
- An IGA score of cleared (0) or minimal (1) at Week 48.

5.3.2. Analysis Methods

The major secondary efficacy analyses described in this section will be performed using the full analysis set. For the major secondary analyses, all non-inferiority tests will be performed 1-sided ($\alpha=0.025$) with a non-inferiority margin of 10%. The margin of 10% was similarly determined as for the primary endpoint. All superiority statistical testing will be performed at a two-sided

significance level of 0.05. In addition, all the major secondary analyses will also be performed on the per protocol analysis set defined in Section 2.4.1.2. The same statistical methods used for the primary endpoint will also be used to analyze the major secondary endpoints. In addition, similar Sensitivity Analyses 1 and 2 as performed for the primary endpoint will be performed for the major secondary endpoints. For the Sensitivity Analysis 2 for the endpoints of PASI 75 response and PASI 90 response at Week 12 where non-inferiority test only is specified for these 2 endpoints, 1-side Wald test with Mantel-Haenszel weights adjusted by investigator site will be performed. The sensitivity analyses using MI will be performed similarly as that done for the primary endpoint including using the same seeds and same number of imputations.

In addition, subgroup analyses for the IGA score of cleared (0) at Week 48 and PASI 100 at Week 48 will be performed similarly as for the primary endpoint.

The major secondary analyses are:

- The non-inferiority test comparing guselkumab with secukinumab for the proportion of subjects achieving a PASI 75 response at both Week 12 and Week 48 will be performed. If non-inferiority is established, the superiority test on this endpoint will be performed.
- The non-inferiority test comparing guselkumab with secukinumab for the proportion of subjects achieving a PASI 90 response at Week 12 will be performed.
- The non-inferiority test comparing guselkumab with secukinumab for the proportion of subjects achieving a PASI 75 response at Week 12 will be performed.
- The non-inferiority test comparing guselkumab with secukinumab for the proportion of subjects achieving a PASI 100 response at Week 48 will be performed. If non-inferiority is established, the superiority test on this endpoint will be performed.
- The non-inferiority test comparing guselkumab with secukinumab for the proportion of subjects achieving an IGA score of cleared (0) at Week 48 will be performed. If non-inferiority is established, the superiority test on this endpoint will be performed.
- The non-inferiority test comparing guselkumab with secukinumab for the proportion of subjects achieving an IGA score of cleared (0) or minimal (1) at Week 48 will be performed. If non-inferiority is established, the superiority test on this endpoint will be performed.

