1.4. Sample Size Justification

This study is designed to evaluate the efficacy of guselkumab 100 mg vs secukinumab 300 mg. The power and sample size were evaluated for the primary endpoint of PASI 90 at Week 48. In addition, since the response rate for guselkumab for PASI 100 at Week 48 is around 50% where the variability is the highest, the power and sample size were also evaluated for this major secondary endpoint. The assumptions for the sample size and power calculations were based on the data from the guselkumab CNTO1959PSO3001 and CNTO1959PSO3002 and the secukinumab Phase 3 studies (ERASURE and FIXTURE).¹ The assumptions used are as follows:

- The proportion of subjects who achieve a PASI 90 response at Week 48 is 70% to 80% in subjects receiving guselkumab and 60% to 70% for subjects receiving secukinumab.
- The proportion of subjects who achieve a PASI 100 response at Week 48 is 44% to 51% in subjects receiving guselkumab and 35% to 40% for subjects receiving secukinumab.

Approximately 1,040 subjects are planned to be randomized in a 1:1 ratio to either guselkumab 100 mg (n=520) (administered at Weeks 0, 4, 12 and q8w thereafter until Week 44) or secukinumab 300 mg (n=520) (administered at Weeks 0, 1, 2, 3, and 4 and q4w thereafter until Week 44).

Based on the above assumptions, the planned sample size, and a noninferiority margin of 10%, the power to demonstrate the non-inferiority for the primary endpoint of PASI 90 at Week 48 and the major secondary endpoint of PASI 100 at Week 48 will be > 99%.

Table 1 provides the power for detecting a treatment difference (superiority of guselkumab over secukinumab) under varying assumptions at a significance level of 0.05 for the primary endpoint PASI 90 at Week 48 and the major secondary endpoint of PASI 100 at Week 48.

Table 1: Power to Detect a Treatment Effect Based on Different Proportions of Subjects Achieving the Primary Endpoint PASI 90 at Week 48 and the Major Secondary Endpoint PASI 100 at Week 48

Secukinumab 300 mg (n=520)	Primary Endpoint PASI 90 at Week 48	
	Guselkumab 100 mg (n=520)	
60%	70%	92%
	75%	>99%
	75%	94%
65%	80%	>99%
	80%	96%
70%	Selected Major Secondary Endpoint PASI 100 at Week 48	
	44%	84%
	45%	91%
	46%	95%
	49%	83%
40%	50%	90%
	51%	95%

PASI = Psoriasis Area and Severity Index.

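### Does the 10-point margin for PASI 100 at Week 48 have to change because it keeps less than 80% of the secukinumab benefit?

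*SAP*

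**What the plan says.** SAP 5.2.3 gives several grounds for the primary margin. The first is clinical: "A non-inferiority margin of 10% was chosen based on a minimal clinically meaningful difference". The second is precedent: the same margin in an ustekinumab psoriasis study and in the two earlier guselkumab Phase 3 studies. The third is retention of effect. The SAP remarks that "placebo response rates for PASI 90 are consistently low" (under 5%) and that no Week 48 placebo data exist, so that "the preservation of benefit for the Week 48 endpoints is based on the historic response rates of the active comparator". It puts the historic secukinumab PASI 90 rate at that visit at 64.6%, with 95% confidence limits of 60.7% and 68.6%, and draws this inference: "whereby a 10% non-inferiority margin would preserve at least 80% of the secukinumab benefit".

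Protocol 11.3.2 and the protocol synopsis give only the clinical difference and the precedent.

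SAP 5.3.2 applies the 10-point margin to all major secondary endpoints with one sentence of rationale, "The margin of 10% was similarly determined as for the primary endpoint". SAP 5.4.2 repeats that sentence for the other secondary endpoints. Neither section gives an endpoint-specific control rate or retained fraction. SAP 1.4 assumes, for PASI 100 at Week 48, "44% to 51% in subjects receiving guselkumab and 35% to 40% for subjects receiving secukinumab".

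**The concern.** The only ground with a number attached is retention of effect, and SAP 5.2.3 introduces it for the Week 48 endpoints in the plural. PASI 100 at Week 48 is one of these, and its planning rate comes from the same two secukinumab Phase 3 studies. A reader who takes the sentence in SAP 5.3.2 at face value could assume that about 80% of the benefit is protected there too. It is not: a fixed 10 points takes a larger share of a 35-40% rate than of a 64.6% rate.

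Non-inferiority on PASI 100 is a separate step in the Type I-controlled sequence of SAP 5.1.1.1. If it passed and superiority then failed, the trial could claim non-inferiority on complete clearance while allowing the loss of a quarter or more of the comparator's effect. Complete clearance is prominent in the design rationale (protocol 3.2), so it is reasonable to ask whether the margin should be tightened.

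**Working it through.** **Inputs.** Margin 10 points, 1-sided alpha 0.025 (SAP 5.3.2). Secukinumab PASI 90 at Week 48: 64.6%, lower limit 60.7% (SAP 5.2.3). Placebo PASI 90: under 5% (SAP 5.2.3). Secukinumab PASI 100 at Week 48: 35-40%; guselkumab 44-51%; 520 per arm (SAP 1.4). No placebo rate for PASI 100 is given, so 0% to 5% is assumed.

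**Step 1: the plan's own figure.** Retained fraction = 1 - margin / (control rate - placebo rate).
- 64.6%, placebo 0: 1 - 10/64.6 = 84.5%
- 60.7%, placebo 0: 1 - 10/60.7 = 83.5%
- 60.7%, placebo 5%: 1 - 10/55.7 = 82.0%

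At least 80% holds for PASI 90 in each case.

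**Step 2: the same formula for PASI 100.**
- 35%, placebo 0: 1 - 10/35 = 71.4%
- 40%, placebo 0: 1 - 10/40 = 75.0%
- 35%, placebo 5%: 1 - 10/30 = 66.7%
- 40%, placebo 5%: 1 - 10/35 = 71.4%

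With zero placebo response, 10 points keeps 80% only if the control rate is at least 10/0.20 = 50%. The planning range lies below that.

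**Step 3: the margin that would keep 80%.** It is 0.20 x (control - placebo): 7 points at 35% and 8 points at 40% with zero placebo, or 6 and 7 points with 5% placebo. A 7-point margin therefore misses 80% at a 35% rate if placebo is 5%: 1 - 7/30 = 76.7%.

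**Step 4: what a tighter margin costs.** Non-inferiority power = Phi[(pG - pS + M)/SE - 1.96], where pG and pS are the guselkumab and secukinumab rates, M is the margin and SE = sqrt[pS(1-pS)/520 + pG(1-pG)/520]. For 40% v 44%, SE = sqrt[(0.2400 + 0.2464)/520] = 0.0306. Ten points gives Phi(0.14/0.0306 - 1.96) = 99.6%, and 7 points gives Phi(0.11/0.0306 - 1.96) = 94.9%.

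| Secukinumab v guselkumab | 10 points | 7 points |
|---|---|---|
| 35% v 44% | >99.9% | 99.96% |
| 40% v 49% | >99.9% | 99.94% |
| 40% v 44% | 99.6% | 94.9% |
| 35% v 35% | 92.2% | 65.8% |
| 40% v 40% | 90.9% | 63.5% |

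The more than 99% power in SAP 1.4 holds at 10 points even for the narrowest pair in the planning ranges (40% v 44%). At 7 points it does not.

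**Step 5: where the two margins would disagree.** With both rates near 35-40%, the half-width of the 95% interval is 1.96 x sqrt[2 x 0.35 x 0.65/520] = 5.8 points, or 6.0 points at 40%. An observed guselkumab deficit of about 1 to 4 points passes 10 points and fails 7. A larger deficit fails both, and a smaller one passes both.

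**The case for a change.** The strongest case for acting is that the mismatch is certain on the SAP's own figures and that correcting the wording costs almost nothing. If the sponsor meant only the clinical-difference ground, SAP 5.3.2 does not say so, and the plural in SAP 5.2.3 points towards retention. Both points stand: the sentence is loose, and a reader could draw the wrong inference for PASI 100.

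What does not stand is the step from loose wording to a wrong margin. SAP 5.2.3 presents the 80% as what 10 points happens to keep for PASI 90, after the clinical difference and the precedent. It does not present it as a threshold from which margins are derived. Read against the clinical-difference ground, the sentence in SAP 5.3.2 is not shown to be false.

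Nor can the point be extended to the other secondary endpoints. The documents give no secukinumab rate for IGA 0, IGA 0 or 1, PASI 75 or the Week 12 endpoints, so no shortfall can be computed and no margin derived for them.

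The 7-point alternative looks nearly free at a 9-point guselkumab advantage. But the scenario that motivates it, non-inferiority without superiority, is one in which the true rates may be close, and there the loss of power is large.

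**Conclusion.** No change follows. The quantified part of the primary rationale does not transfer to PASI 100 at Week 48: retention is at most 71.4-75.0% against 82.0-84.5% for PASI 90. The margin also rests on a clinical difference and precedent, and the test procedure and stated power are sound as written.

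Tightening the margin is a debatable trade-off rather than a correction. It would give up roughly 26 to 27 points of power at equal true rates (92.2 - 65.8 = 26.4; 90.9 - 63.5 = 27.4) for a criterion the SAP does not set for this endpoint, and 7 points would still miss that criterion at a 35% rate with 5% placebo. Rewording the rationale would annotate one sentence and change no analysis.

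The practical exposure is small. PASI 100 is fourth among the major secondary endpoints, tested confirmatorily only after superiority on the primary endpoint and success on the preceding analyses. It has its own superiority test. Because SAP 5.3.2 applies the primary methods to it, the difference will be reported with its 95% confidence interval, from which the possible loss can be read directly.

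These figures rest on the 35-40% planning range, which is not a confidence interval, on an assumed placebo rate of 0-5% for PASI 100, and on an unstratified normal approximation for power. A control rate below 35% would lower retention further without altering the conclusion.
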